**Endpoints:**

*Primary Endpoints:*

*Imaging (7T) – Tasking based activation to Monetary Incentive Delay (MID) Task; Task based activation to Emotion Reactivity task (Hammer)  
Behavioral/Observational:-Probabilistic Reward Task (PRT) and EffortExpenditure for Reward Task (EEfRT); Changes in SHAPs scores pre/post treatment*

*Secondary & Exploratory Endpoints:*

*Imaging (7T)- Resting state connectivity  
Behavioral/Observational -CGI-I; Homework Completion (participation and clinician-rated); ecological momentary assessment of activation, mood, reward experiences. Passive location tracking (PLT) data via the MetricWire app for the EMA sub-study to compare distance traveled before and after both treatments as a secondary, exploratory measure of behavioral activation. Follow-up analyses will evaluate relations between motion tracking, behavioral, brain, and clinical measures of response to both treatments.*

*PET Aim1: Extract dynamic change in binding potential (BPND%) before, during and after the task and then comparing these values before and after treatment between treatment groups. PET Aim2: Correlations between changes in PET striatal binding potential magnitudes and changes in fMRI.*

Study Population:	This study will recruit participants with clinically significant anhedonia, who are 18-50 years old who are able to read & understand English, and who are seeking treatment.
Phase:	Phase I/II
Description of Sites/Facilities Enrolling Participants:	Recruitment and therapeutic intervention for the study managed by Duke University Medical Center, Department of Psychiatry and Behavioral Sciences and Duke PI ;Eligible participants based on the initial Duke study assessment consent at UNC-Chapel Hill in the Department of Psychiatry under UNC PI for all 7T imaging, EMA and optional PET Scans.

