**Aims 3, 4, and 5 pertain to all 210 participants randomized (n=105 to receive BATA and n=105 to receive MBCT).**

Aim 3: We predict that BATA will produce clinically and statistically significant improvements in anhedonia and functional outcomes that exceed those due to the comparison treatment.

Aim 4: We predict that BATA will improve behavioral indices of reward sensitivity.

Aim 5: To evaluate the effects of BATA versus a comparison treatment on neural response to rewards. We predict that, consistent with Aim 1, BATA will increase right CN activation during reward anticipation and decrease rACC activation during reward outcomes and that BATA will not decrease amygdala activation to threat, confirming the specificity of BATA for targeting these positive valence neural systems. This Aim will provide a replication and extension of Aim 1 findings with a larger sample and with an optimal treatment dose.

In the PET sub-study, Hypothesis 1- BATA, but not the comparison treatment, will result in increased phasic striatal DA release but will not influence background DA striatal tone. Hypothesis 2- that normalization of fMRI-derived mesocorticolimbic activation due to BATA specifically will be associated with increased phasic DA release but no change in background DA tone during incentive processing.

This is not a pilot study but rather a Phase I/II study. The R61 phase (Phase I) of the protocol is designed to provide preliminary data for the acceptability, identification of the optimal dose of BATA as well as the preliminary efficacy of BATA in subjects with anhedonia compared to those in the MBCT control group. Using the fMRI data, this phase of the study will test if BATA produces changes in neural responses to reward anticipation and reward outcomes that exceed changes in the MBCT group and does not impact neural responses to threat. As such, a small group (N = 60) of subjects will be in this blinded phase and they will complete up to a total of 4 fMRI scans (pre-treatment, week 8, 12 and post-treatment). The R61 study will be entering a no-cost extension at the end of the current project period to allow for completion of data collection for this phase. Due to limited funds, the number of scans obtained is being reduced from up to 4 scans to two scans (pre- and post-treatment.) for participants

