## 9 STATISTICAL CONSIDERATIONS

### 9.1 SAMPLE SIZE DETERMINATION

**Aims 1, 2, and 5:** To evaluate whether BATA produces changes in neural responses to reward anticipation and reward outcomes that (1) exceed our *a priori* target engagement criteria; (2) exceed changes due to a comparison treatment; and (3) does not impact neural responses to threat. To evaluate relations between BATA dose and neural target engagement by examining changes in reward responding with fMRI scans 8, 12 and 16 weeks after starting the 15-week treatment.

Power is calculated for Aim 1 fMRI analyses because of its smaller sample, and the Aims that involve all 210 participants will have higher power because of the larger sample and optimized BATA dose. For Aim 1 we will enroll 30 outpatients per group to have complete data from 25 per group. Based on our pilot data demonstrating increased right CN activation during reward anticipation and decreased rACC activation during reward outcomes, we calculated an effect size of approximately  $z=4.1$ . Conservatively, we estimate the effect size for the increased right CN activation and reduced rACC activation will be in the range of  $z = (0.75-1.25)$ . Our models will thus have  $>90\%$  power at  $\alpha=0.025$ .

**Aims 3 and 4:** To evaluate the effects of BATA versus MBCT on anhedonic symptoms, functional outcomes, and behavioral indices of reward sensitivity. Our power analysis addresses the effects of BATA versus MBCT on SHAPS scores (conducted with Gpower) as an ANCOVA with two groups and two timepoints. With 65 subjects per treatment group with complete data at post-treatment,  $\alpha = .05$ , and assumed correlation between assessments of 0.35 (based on preliminary studies), we will have 98% power to detect small ( $f = .2$ ) effects. Pilot data in depressed patients indicated a large effect from pre-to post-treatment ( $d=1.24$ ,  $f = .62$ ), and we are powered to detect these effects. We are 80% powered to detect the interactions with effects as small as  $f = .14$ .

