**Aim 2:** We will analyze whether dose moderates treatment response via regression models that predict change in neural target (CN and dACC) activation from the number of sessions as an indicator of BATA dose. Hierarchical linear modeling where time-in-weeks is treated as a continuous variable nested within subject will provide parameter estimates of the linear, quadratic, and cubic functions for change over time in neural target engagement over the course of treatment. Standard evaluation (e.g., significant at  $p < .05$ ) will guide our selection of the most appropriate function. From these functions, we can estimate both the point in time where the change in target engagement is greatest and where it approaches 0, meaning minimal further improvement is anticipated. Although mid-treatment scans will occur at weeks 8 and 12, we will estimate change continuously so the optimal dosage is not restricted to one of those timepoints.

**Aims 3 and 4:** To evaluate the efficacy of BATA, relative to MBCT, for treating anhedonia, functional outcomes, and behavioral indices of reward sensitivity, we will test for differential change over time between those who receive BATA and those who receive MBCT post-treatment. We will use an intent-to-treat (ITT) analysis for patients who receive BATA relative to those who don't. The ITT model will be a repeated-measures ANCOVA with effects for treatment condition (BATA, MBCT), outcome measure (SHAPS, PRT, etc), time (pre-treatment, post- treatment) and their interactions. The interaction tests will assess mean differences at each time point as well as differences in the degree of change between the groups. This also provides tests of each group relative to their baseline scores. We will include gender and age as covariates in these models. \*\*We will also note any participants who were enrolled in the study and had PRT & EffRT reward tasks data omitted during COVID-19 times.

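### As worded, the Aims 3 and 4 model makes outcome measure a crossed factor, so the SHAPS-only power is not guaranteed for its interactions and a PRT-only benefit could go unseen

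*Combined protocol and SAP*

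**What the plan says.** Section 9.2, Aims 3 and 4, gives the model: "The ITT model will be a repeated-measures ANCOVA with effects for treatment condition (BATA, MBCT), outcome measure (SHAPS, PRT, etc), time" (pre- and post-treatment), together with the interactions of these effects. On how it will be read, the section says "The interaction tests will assess mean differences at each time point as well as differences in the degree of change between the groups", and then "We will include gender and age as covariates in these models". It does not mention a common scale or the direction of the measures, it leaves the list of measures open, and it names no interaction as decisive.

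Section 9.1 sizes Aims 3 and 4 on "the effects of BATA versus MBCT on SHAPS scores (conducted with Gpower) as an ANCOVA with two groups and two timepoints", with 65 completers per arm, alpha 0.05 and a correlation of 0.35 between assessments. It states 98% power at f = 0.2, and adds "We are 80% powered to detect the interactions with effects as small as" f = 0.14.

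The synopsis lists as primary behavioural endpoints "Probabilistic Reward Task (PRT) and EffortExpenditure for Reward Task (EEfRT); Changes in SHAPs scores pre/post treatment". Section 4.1 gives the predictions. For Aim 3 it reads: "We predict that BATA will produce clinically and statistically significant improvements in anhedonia and functional outcomes that exceed those due to the comparison treatment". For Aim 4: "We predict that BATA will improve behavioral indices of reward sensitivity".

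**The concern.** When outcome measure is a crossed factor, the treatment-by-time term averages the treatment effect over the measures. The three-way term shows only that the measures moved differently. Neither is the contrast on one endpoint that Aim 3 or Aim 4 asks about.

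The measures also appear to run in opposite directions. Section 5.1 treats a high SHAPS score as clinically significant anhedonia, so benefit is a fall. Section 4.2 describes the PRT as measuring a response bias induced by reward, so improved reward sensitivity is naturally read as a rise. The documents give no PRT scoring, so that direction is an inference.

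Three things therefore stay open until after the data are seen: the scaling, the measures included, and the interaction reported. Each can change the conclusion. There is also a practical risk. The COVID-19 provisions allow the computer tasks to be omitted while self-report continues, so a joint model fitted to complete cases would drop those participants from the SHAPS comparison too.

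**Working it through.** **1. Reproduce the plan's power.** Inputs from section 9.1: N = 2 × 65 = 130, m = 2 timepoints, ρ = 0.35, alpha 0.05. For the group-by-time interaction, λ = f²·N·m/(1 − ρ) on 1 and 128 df.

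- f = 0.2: 0.04 × 260/0.65 = 16.0, power 0.978 (stated 98%).
- f = 0.14: 0.0196 × 260/0.65 = 7.84, power 0.794 (stated 80%).

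A between-group test of the same design gives 0.787 at f = 0.2, and a plain ANCOVA gives 0.619. The stated figures therefore belong to a one-outcome treatment-by-time interaction. In SD units the difference in change is 4f, so 0.56 SD and 0.80 SD. Check: the variance of change is 2(1 − 0.35) = 1.3 SD², and 0.80²/(1.3 × 2/65) = 16.0.

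**2. Joint model.** Work with the change scores. Treatment-by-time uses weights c = (½, ½) over two outcomes and the three-way term uses c = (1, −1). Then λ = (c′δ)²/(c′Σc × 2/65) on 1 and 128 df, ignoring the covariates. Not in the documents and therefore assumed: r = 0.35 for every measure; SHAPS/PRT SD pairs 4/0.3, 6/0.2 and 8/0.1; correlation between outcomes −0.4 to 0.2 unless stated; PRT benefit is a rise.

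*(a) Raw units, SHAPS and PRT only.*

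- PRT-only benefit of 0.80 SD. Example with SDs 4 and 0.3, correlation 0: mean effect ½ × 0.80 × 0.3 = 0.12; variance ¼ × 1.3 × (16 + 0.09) = 5.23; λ = 0.0144/(5.23 × 2/65) = 0.09. Over all pairs and correlations, power is 5-6% in either interaction, against 98% in a PRT model.
- SHAPS benefit of 0.56 SD, PRT unaffected: treatment-by-time 78-82%, three-way 77-80%. At 0.80 SD both are 97-98%.
- SHAPS and PRT both improve by 0.56 SD, signs not aligned: treatment-by-time 71-79%, three-way 80-86%.

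For SHAPS, then, section 9.1's figures survive approximately here. The loss falls on Aim 4.

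*(b) Standardised scores.*

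| Benefit | Signs | Treatment-by-time | Three-way |
|---|---|---|---|
| 0.56 SD on both | not aligned | 5% | 91-99% |
| SHAPS 0.56, PRT 0.28 SD | not aligned | 15-25% | 70-91% |
| 0.56 SD on both | aligned | 95-99.9% | 5% |

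A SHAPS-only model gives 79% for the same 0.56 SD.

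*(c) Raw units, one more measure in the open list*, with 1, 2 or 3 times the SHAPS SD; SHAPS benefit 0.56 SD; treatment-by-time test:

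| SD ratio | Added measure unaffected, correlation 0 | Range at correlation −0.2 to 0.2 |
|---|---|---|
| 1 | 50% | 43-59% |
| 2 | 24% | 21-27% |
| 3 | 14% | 13-16% |

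If the added measure also improves in the same direction (correlation 0 to 0.2), power across these ratios is 91-98% for a 0.56 SD benefit on it and 55-84% for 0.28 SD.

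*(d) Simple effects within the joint model*, raw units, 20,000 simulated trials per case, correlation −0.2 and 0.2. With each outcome's own error term, a PRT benefit of 0.80 SD has 98% power and the SHAPS false-positive rate is 5%. With one error term pooled over outcomes, PRT power is 0% and the SHAPS false-positive rate is 16-17%. On standardised scores the pooled test gives 98% and 5%.

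**The case against.** The strongest reply is that one model per outcome may be what is meant. Section 9.2 aims to test differential change between arms, which is treatment-by-time; it refers to the models in the plural; and section 9.1 describes SHAPS alone at two timepoints. That reading is reasonable, and under it the remaining fault is wording. It is not secure, because outcome measure is listed as an effect with interactions. Section 9.2 also builds Aims 1 and 5 the same way, with brain region as a factor, though there the levels are listed and post-hoc comparisons are named.

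Second, a reader might infer that section 9.1's power is wrong, or has no bearing on the joint model. The documents do not support that. The arithmetic is right for the test it describes, sizing a trial on one key outcome is ordinary practice, and case (a) shows the SHAPS figures holding approximately in raw units. Nor is joint-model power always lower: the three-way term can exceed the SHAPS-only figure.

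Third, the low figures in (b), (c) and (d) rest on adverse choices that the plan does not make: standardising without aligning signs, adding a wholly unaffected measure although Aim 3 predicts functional improvement, and pooling error across raw scales. This stands. The cases show what the wording permits and do not forecast this trial's power.

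**Conclusion.** The point holds in a limited form and should be fixed. As written, the Aims 3 and 4 model leaves scale, sign, list of measures and deciding interaction open, and the 80% and 98% in section 9.1 are secured only for a SHAPS-only treatment-by-time test. In the joint model's interactions the result depends on those open choices. With SHAPS and PRT alone in raw units, power at 0.56 SD on SHAPS stays at about 71-86%, while a 0.80 SD PRT-only benefit is nearly undetectable (5-6% against 98%). Under less favourable but permitted choices, treatment-by-time power at 0.56 SD on SHAPS runs from 59% down to 5%.

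The SDs, the cross-outcome correlations and the effects on measures other than SHAPS are assumed, and the PRT direction is inferred. It would go too far to say that the joint model will certainly be fitted or that the trial is underpowered for SHAPS. Confidence is medium because the one-model-per-outcome reading remains open.

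**What to change.** Drop outcome measure as a factor. Fit one treatment-by-time model per named outcome, on its own scale, using every participant with that outcome. Name SHAPS treatment-by-time, pre to post, at 0.05 as the deciding Aim 3 test; this matches section 9.1 and keeps its stated power. Name the functional outcomes, and analyse them, PRT and EEfRT in separate models. Make any joint model secondary, on sign-aligned scores standardised by baseline SD.

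The cost is plan wording and a few more model runs, with no new data. Whether to control multiplicity across PRT and EEfRT is a separate choice for the sponsor; Holm is one option. Holding each task to 0.025 would lower power at 0.56 SD from 79% to 70% and at 0.80 SD from 98% to 96%. The difference detectable with 80% power would rise from 0.565 to 0.623 SD.

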## 1.3 SCHEDULE OF ACTIVITIES (SOA)

## TIMELINE OF STUDY ASSESSMENTS AND PROCEDURES:

Assessment/Procedure	Online/Phone Screen	Remote/In Person Screen (at Duke) - can be split in 1-2 visits (part remote/part in-person)**	Pre-Tx fMRI (at UNC)	Intervention therapy sessions at Duke) 	Wks 4, 8 & 12 (if applicable) 	fMRI (wk 8 & 12) 	Study Completion Visit-Part I (Duke)	Part II Post-Tx fMRI (UNC)
Online/Phone Screen Questionnaire	X							
Informed consent		X (via Duke REDCap econsent)	X (UNC specific consent)					
SHAPS	X	X	X	X	X	X	X	X
C-SSRS		X			X (post)		X (post)	
SCID5 relevant to inclusion /exclusion, NART		X						
SCID-5-RV		X						
[name] & Background info, CGI-S, CTQ		X						
R61 Phase: BDI-II, BAI, SF-36, PhenX depression & perceived stress, PCL-5, PSWQ, IDAS, TMS, SRS-2		X			X		X	
R33 Phase: BDI-II, BAI, SF-36, PhenX depression & perceived stress, PCL-5, PSWQ, TMS, MAPS, IDS-RS, BADS		X			X		X	
R33 Phase: WAI					X		X	
EEfRT, PRT		X			X		X	
Caffeine, Nicotine, Alcohol & sleep day of intake		X	X		X	X	X	X
Urine Pregnancy Test; PEERS (female only)			X (pre)			X (pre)		X (pre)
CGI-I, % homework tasks completed				X			X	
MID			X 			X		X
fMRI			X 			X		X
MRI checklist			X			X		X
Urine Drug Screen		X**						
Acceptability Questionnaire							X	

Between 8-15 weeks of therapy sessions (therapy will be either MBCT or BATA), in-person or remote during COVID-19 guidelines.

At visits week 4, 8 & 12 (if applicable), subjects will complete EEfRT & PRT computer tasks at the beginning of the visit followed by the therapy session or if during COVID-19 times, at a separate in-person visit from the remote therapy session. All paperwork done at therapy visits will be done in addition to procedures noted in this column. They will then complete the REDCap questionnaires at these key assessment time points (either in-person or done remotely by REDCap survey invitation). If the final therapy visit is before week 8, there will be three assessment points (pre-treatment, week 4, and at the last therapy visit). If the final therapy visit is between week 8 and week 12, there will be four assessment points (pre-treatment, week 4, week 8, and at the last therapy visit). If the final therapy visit is after week 12, there will be five assessment points, and post-treatment assessments will be administered either at the last therapy session or separately if therapy was remote. COVID-19

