#### **Treatment (at Duke between 8-15 weeks)**

Patients will complete a course of BATA or MBCT. Subjects will be assigned a specific Duke study therapist and will continue with the same therapist through the 8-15 weeks of therapy. All therapy sessions will occur in Duke CBRTP located in the Civitan building ([name]) or via WebEx/Zoom Duke approved remote platforms. At the end of each therapy visit, the therapist will complete the Clinical Global Impairment scale in relation to improvement of symptoms (CGI-I) and the subject will complete the SHAPS. Starting at the second therapy session, the subject will be asked to give a % of how much of the homework tasks they had completed over the prior week since the last therapy session. The weekly therapy sessions will last around 1 hour, except for weeks 4, 8, 12, and the final therapy session (if not at week 8 or 12) as noted just below. All remote weekly therapy sessions will last around 1 hour.

Weeks 4, 8, and 12 (if applicable) : At these specific therapy visits, subjects will also be asked to complete the EEfRT and PRT computer tasks again. The tasks will be done and the subject will be asked about their caffeine, alcohol, nicotine & sleep habits over the past day in addition to completing SHAPS & % homework tasks completed over the past week (if not already completed during the therapy session). The subject may have their therapy session before or after these tasks & surveys or may be completed on a separate day during the week 4, 8, and 12. The C-SSRS will be administered after the computer tasks. They will then again be asked to complete most of the questionnaires they completed at the screening assessment visit (i.e. R61: the PSWQ, PCL-5, BDI-II, BAI, SF-36, IDAS, TMS, SRS-2, and PhenX measures of related to depressed mood and perceived stress, R33: the MAPS, IDS-RS measures related to anhedonia, BADS, WAI, PSWQ, PCL-5, BDI-II, BAI, SF-36, TMS, and PhenX measures of related to depressed mood and perceived stress). They will complete them directly in REDCap either in-person or by REDCap survey invitation. These visits will last from 2 to 2 ½ hours.

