Therapy sessions are provided at no cost to the participant and they will be given a parking pass, if applicable. At weeks 4, 8, & 12 of therapy, they will complete the computer effort/reward tasks & will receive between \$12-19 (\$10 + \$2-9 based on task performance) at each of those 3 visits for a total of \$36-57 at these 3 therapy visits in addition to parking or bus pass. **Again, during COVID-19, if tasks cannot be conducted at an in-person visit, the participant would still be paid the minimum of \$12 for these visits, if applicable.**

UNC: For completing each MRI brain scan visit, subjects will receive \$75 up to as much as \$110 depending on their responses to the scanner task plus a parking or bus pass, if applicable. Thus total fMRI compensation for the study will be between \$150-440. **Participants enrolled at UNC as of 11/1/18, will only have a pre & post treatment MRI scan and thus total fMRI compensation for the study will be between \$150-220.**

Based on our previous experience, retention for psychotherapy trials from pre- to post-neuroimaging sessions is approximately 81%.

**EMA Optional Sub-study:** Participants will be compensated \$10 per week of EMA participation, and will receive a bonus of \$1 per survey completion if they complete more than 8 responses in a given week. Thus, participants will have the potential to earn up to \$52 over the course of the four weeks of EMA. In the 1st phase of the study- a R61 no cost extension & due to limited funds-participants who enrolled in the 1st phase on or after 11/1/18, have been completing EMA after pre and post MRI scans & thus can earn up \$26 over the course 2 weeks of EMA instead of \$52.

**R33 EMA compensation:** **With the additional wks 4, 8, and 12 (if applicable) adding to the pre and post treatment scan timepoints, participants who agree to the optional EMA portion of the study, will have the potential to earn up to \$65 over the course of 5 weeks of EMA instead of only \$26 from the R61 no cost extension.**

**PET sub-study:** Subjects will be compensated a range of \$160 - \$200 per scan, to be determined by the computer activity that they complete while in the scanner. If they are unable to complete the PET imaging with computer activity after getting in the scanner, they will be paid \$20/hour for that session.

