Exploratory Connectivity Analyses: Mesocorticolimbic connectivity in central to anhedonia. We will explore task-dependent correlations between ROIs using a psychophysiological interactions approach as in our prior work. Timeseries will be extracted from ROIs using FSL Featquery for each participant and trial type and correlation values will be transformed using a Fisher r-to z transformation. We also conduct whole-brain connectivity analysis, with a particular emphasis on the salience network (i.e., dorsal anterior cingulate cortex, anterior prefrontal cortex, and anterior insula), by segmenting the brain based on a probabilistic atlas, while correcting for multiple comparisons at the familywise error rate of  $p < .05$ .

**Secondary Analysis:** Secondary data analysis will be conducted examining relationship between psychological symptoms and patterns of brain activation in the functional neuro data. Data will be transferred from UNC to Duke to be analyzed by Duke study team members.

**Aims 1 and 5:** Only patients who complete baseline measures will receive BATA, and those who complete at least one BATA session will participate in post-treatment assessments (ITT, estimating ~90% of sample). We will compare fMRI activation in regions of interest at pre- and post-treatment. Primary analyses will address changes in regional brain activation from baseline to post-treatment.

Models will include motion parameters, gender, and age as covariates. The design is a 2 (BATA vs MBCT) X 3 (CN, rACC, amygdala) X 2 (pretreatment vs post-treatment) ANCOVA testing the change from pre- to post-treatment as moderated by treatment group and brain region in the outcome variables controlling for the covariates. Post-hoc comparisons will compare change across each region. Note that CN and rACC activation values are derived from the MID task whereas amygdala activation values are derived from the threat task.

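### For Aims 3 and 4, the pre/post ANCOVA has no method for missing post-treatment values and leaves the SHAPS scores from every therapy session unused

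*Combined protocol and SAP*

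**What the plan says.** **Model.** Section 9.2, Aims 3 and 4, calls the analysis intention-to-treat and specifies: "The ITT model will be a repeated-measures ANCOVA with effects for treatment condition (BATA, MBCT), outcome measure (SHAPS, PRT, etc), time (pre-treatment, post- treatment"), plus interactions, with gender and age as covariates. The SHAPS endpoint in the Synopsis is "Changes in SHAPs scores pre/post treatment".

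**Missing data.** The Aims 3 and 4 paragraph says only that participants with "reward tasks data omitted during COVID-19 times" will be noted. Section 6.1.2 classes uncollected week 4, 8 and 12 assessments as missing and goes no further. No section names an imputation, likelihood-based or sensitivity method.

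**Data collected.** Every session yields a SHAPS score: "the therapist will complete the Clinical Global Impairment scale in relation to improvement of symptoms (CGI-I) and the subject will complete the SHAPS" (Section 4.2, Treatment; also Section 1.3). Hierarchical linear models are planned in Section 9.2, but only for Aim 2 and the EMA data.

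**Expected loss.** Section 9.1 bases power on this: "With 65 subjects per treatment group with complete data at post-treatment". Section 3 ties Aims 3 to 5 to all 210 randomised, 105 per arm. Section 5.4 says "retention for psychotherapy trials from pre- to post-neuroimaging sessions is approximately 81" percent. Section 9.2, Aims 1 and 5, says those with at least one BATA session "will participate in post-treatment assessments (ITT, estimating ~90% of sample").

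**Recovery of late values.** The last therapy visit is an assessment point: "If the final therapy visit is between week 8 and week 12, there will be four assessment points" (Section 1.3, note 2; Section 4.2 repeats this and also covers a last visit before week 8). Sections 4.2 (Neuroimaging session) and 7.1 ask people who drop out before week 8 to return.

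**Removal.** Sections 2.3.3, 6.5 and 7.2 provide for removal after symptom worsening or when a disallowed medication is needed.

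**The concern.** A repeated-measures ANCOVA on two time points, fitted in the usual way, uses complete pre/post pairs. The comparison then rests on people who have a post value, which does not fit the intention-to-treat label. If leaving is related to SHAPS, and the loss rate or the reasons differ by arm, the difference in change is biased. Equal loss rates do not rule this out. Some removal is tied to symptoms by the protocol's own rules, so loss unrelated to outcome cannot be taken for granted.

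Two features add to the problem. Therapy may end anywhere from week 8 to week 15, partly according to clinical response (Sections 6.1.2 and 6.4), so post is not a fixed time, and no rule covers a score taken at removal. Outcome measure is also a factor in the stated model. If it is fitted as one joint model, a participant whose reward task was omitted could be lost from the SHAPS comparison as well, although Section 4.2 keeps the self-report in that case.

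The in-treatment SHAPS scores are the data most likely to explain who leaves, and they are already being collected.

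**Working it through.** **1. Reproduce the plan's power.** Inputs from Section 9.1: 65 complete per arm (N = 130), two time points (m = 2), correlation 0.35, alpha 0.05. For the group-by-time interaction, the noncentrality is f² × N × m / (1 − 0.35), on 1 and N − 2 degrees of freedom.
- f = 0.2: 0.04 × 130 × 2 / 0.65 = 16.0, power 97.8% (stated 98%).
- f = 0.14: 0.0196 × 130 × 2 / 0.65 = 7.84, power 79.4% (stated 80%).

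The plan's figures therefore describe a two-time-point interaction in complete pairs.

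**2. Power with other numbers of pairs, f = 0.14.**
- 85 per arm (81% of 105), N = 170: noncentrality 10.25, power 88.9%.
- 68 per arm (85 less an assumed 20% with no post-treatment PRT), N = 136: noncentrality 8.20, power 81.1%.

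**3. Scale for bias.** The SD of change is √(2 × (1 − 0.35)) = 1.140 SD of the score. Under this formula f = 0.14 is a between-arm difference in change of 4 × 0.14 = 0.56 SD of the score, and 0.56 / 1.140 = 0.49 SD of change.

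**4. Null simulation.** From the plan: 105 per arm, correlation 0.35 between baseline and week 15, improvement of 1.24 SD (the Section 9.1 pilot effect, applied to both arms). Assumed: scores at weeks 0, 4, 8, 12 and 15 with correlation 0.35^(gap/15); removal after week 4, 8 or 12, correlated 0.3 to 0.8 with SHAPS change so far; best responders finishing at week 8 or 12; and all loss rates. There were 4,000 trials per scenario. Bias is in SD of change.

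| Loss | Pre/post pairs: bias | Type I error |
|---|---|---|
| 19% v 19%, worst scorers leave both arms (correlation 0.3, 0.5) | within 0.001 | 5.0% |
| 15% v 23%, worst leave both arms | 0.03-0.06, favouring the arm that loses more | 5.7-8.3% |
| 15% v 23%, best leave both arms | 0.02-0.06, the other way | 4.9-7.6% |
| 19% v 19%, worst leave one arm, unrelated in the other | 0.07-0.16 | from 8% up |

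A mixed model with arm-by-occasion means, unstructured covariance and post as its own occasion had bias of at most 0.013 and type I error of 4.4-5.8% in the scenarios where it was fitted and removal depended on observed scores.

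Counting the last visit before removal as post gave bias of 0.05-0.06 against the arm that loses more at 15% v 23% (worst leave; type I error 6.5-7.6%). In the one-arm scenario it gave 0.02-0.05 (5.1-7.2%).

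**5. Sensitivity to the assumptions.** A second simulation used correlation 0.35 with baseline, 0.5-0.7 between later visits, and about 80% retention. One-arm outcome-dependent loss gave 0.028-0.069 SD of the score; divided by 1.140, this is about 0.02-0.06 SD of change. Bias was near zero when loss worked alike in both arms, and a likelihood model stayed within 0.01 SD throughout.

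**6. If leaving depends on the next, unseen score.** The mixed model's bias was 0.02-0.10 SD of change (type I error 5.3-13.6%), against 0.04-0.21 for pairs.

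**The case against.** The strongest reply is that the plan limits the loss and that any bias may be negligible. Drop-outs before week 8 are asked back, the last therapy visit is an assessment point even when it falls early, and the removal rules are the same for both arms. The 10% worsening rule in Section 2.3.3 concerns depression, anxiety and trauma symptoms, not SHAPS. If loss works alike in both arms at equal rates, bias is essentially zero. All of this stands. It limits the size but supplies no analysis method, and no section says whether a score taken at removal is the post value.

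It is also fair to say that a pre/post analysis matches the stated endpoint, and that leaving in-treatment scores out is partly a choice about efficiency. With 19% loss unrelated to SHAPS and a true difference of 0.6 SD, simulated power was 86.6% for pairs and 89.9% for the mixed model, a modest gain.

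Four stronger readings are tempting, but the documents do not support them:
- *The trial expects to lose 38%.* 65/105 is 62%, but no section presents 65 as the expected number of completers out of 105. It is also 87% of the 75 per arm in the R33 phase. The stated expectations are 81% (imaging) and about 90% (Aims 1 and 5).
- *Type I error could reach 28%.* That needs the strongest assumed link between SHAPS and removal in one arm and none in the other, or 38% loss. Nothing in the documents predicts either.
- *Dropping SHAPS values when PRT is missing would leave the trial underpowered.* By the plan's own formula, 68 pairs per arm still give 81.1% at f = 0.14. Section 9.1 powers SHAPS alone and Section 9.2 speaks of models in the plural, so separate fits may already be intended.
- *The wording about receiving BATA means an as-treated analysis.* Sections 3 and 4.1 tie these aims to everyone randomised.

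**Conclusion.** The point holds and should be fixed before the arms are compared. The plan names an intention-to-treat analysis, anticipates missing post-treatment values, gives no method for them, and leaves unused the scores best placed to deal with them.

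The likely size is modest. With the same mechanism in both arms and 15% v 23% loss, a bias of 0.02-0.06 SD of change is about 4-12% of the 0.49 SD difference at f = 0.14. Larger bias needs loss that relates to SHAPS in one arm only. The documents give no loss by arm or by reason, so direction and size in this trial cannot be known. The loss rates, removal mechanisms and finishing times are assumptions. The stated power figures are correct for complete pairs and are not in dispute.

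**What to change.** 1. **SHAPS.** Make the main analysis a likelihood-based mixed model by randomised arm, using baseline and all collected post-baseline scores (each session, weeks 4, 8 and 12, final). Keep the pre-to-post change contrast as primary. State before analysis how post is placed given 8 to 15 weeks of therapy, for example the final-visit score as its own occasion whatever the week. State also whether a score taken at removal counts as post, and reconcile that rule with Sections 1.3 and 4.2, which put the final assessment at the last therapy visit.
2. **Other outcomes.** Fit each outcome in its own model, as the SHAPS-only power calculation implies, using the week 4, 8 and 12 values where collected. An omitted PRT or EEfRT then cannot remove a SHAPS value.
3. **Sensitivity and reporting.** Keep the pre/post ANCOVA as a sensitivity analysis, and report loss by arm and reason. Add a sentence that all randomised participants with a baseline value are analysed in the arm assigned.

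**Cost.** No new visits or data. The model assumes data are missing at random given the observed scores, and some bias remains if that fails. With weekly scores, a fallback covariance structure must be named in advance. Participants with no session contribute only a baseline score, and the outcomes other than SHAPS have at most three in-treatment values. The document is dated October 2023, late in the trial, so the change needs a documented reason before the arm comparison is analysed. The clinical withdrawal rules are not questioned.
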